Nicotine administration: Nicotine bitartrate will be obtained from Interchem Corporation, Paramus, NJ, and solutions for IV injection will be prepared by U.S. Specialty Formulations, Bethlehem, PA. On the morning of each test session, weight-adjusted nicotine and saline solutions will be prepared by the West Haven VA research pharmacy. Nicotine and saline will be administered using an infusion pump connected to an IV catheter located in a forearm vein. We have followed these procedures in our previous studies, which were completed without any serious adverse effects attributed to nicotine or other safety concerns. [name] holds an ITP (Investigational Tobacco Product) for IV nicotine administration. A new ITP application has been submitted to the FDA for this project.

In each test session, there will be a total of 3 infusions. Each infusion duration will be 10 minutes long, which will be achieved by infusing saline for the remainder of the time following the 2.5- and 5-minute nicotine infusions. A research nurse, will program 2 infusion pumps to administer nicotine or saline solutions. For the 2.5 and 5 min infusion conditions, participants will first receive nicotine for 2.5 and 5 minutes, followed by saline infusions. For the saline condition, participants will receive saline for 10 minutes. The participants will be blind to the randomization. The order of infusions will be: 1) 5-min or 2.5-min nicotine infusion, 2) saline infusion and 5-min or 2.5-min infusion. This infusion order was chosen to minimize carry over effects between nicotine infusions. Participants will be blind to the order of nicotine infusions.

Justification for the nicotine doses and infusion rates: The total nicotine dose for each test session will be 2 mg/70 kg body weight, a dose within the range of nicotine delivered by smoking 1 or 2 tobacco cigarettes or e-cigarettes (21). For safety reasons, the maximum dose of nicotine for each infusion will be 1 mg. The infusion rates will be 0.096 and 0.048 $\mu\text{g}/\text{kg}/\text{second}$ over 2.5 and 5 minutes, respectively.

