Medical monitoring: Participants will be given a thorough physical examination prior to study entry. For nicotine administration sessions, participants will be attached to a cardiac monitor as well as a blood pressure and heart rate monitoring device. An IV catheter for nicotine delivery will be in place throughout each test session. Participants will be administered nicotine only if the systolic blood pressure is <150 mmHg and heart rate is <90 beats/minute. Participants will be terminated from the study if the blood pressure at any time is >170/110 mm Hg, if the heart rate is >130 beats/min, or if they develop signs and symptoms consistent with nicotine toxicity. We have not encountered any cases of nicotine toxicity in our nicotine infusion studies. These study procedures were developed as part of our Investigational Tobacco Product (ITP) application to the FDA for IV nicotine.

Overview of the study: We propose a placebo-controlled study that will recruit male and female menthol nicotine dependent smokers. Following screening and evaluation as described above, eligible participants will be enrolled in the study which will last about 4 weeks. Eligible, participants will be randomized to menthol or non-menthol smoking condition for 2 weeks (Phase 1) and then will be switched to the alternative condition for another 2 weeks (Phase 2). The smoking condition will be open label. Participants will be provided with free cigarettes in Phases 1 and 2. For the menthol condition, participants will be provided their usual brand of menthol cigarettes and for the non-menthol condition, they will be provided a matched-brand non-menthol cigarette (e.g., Newport Non-Menthol Gold 100s for those who smoke Newport Menthol Gold 100s). In week 2 of each Phase, participants will have a test session. Each session will include 3 infusions in the following order: nicotine (1 mg per 70 kg body weight to a maximum dose of 1 mg) delivered over 2.5 or 5 minutes, saline delivered over 10 minutes, and nicotine (1 mg/ 70kg to a maximum dose of 1 mg) delivered over 2.5 or 5 minutes). For safety reasons, the maximum dose of nicotine for each infusion will be 1 mg. The infusion rates will be 0.096 and 0.048 µg/kg/second over 2.5 and 5 minutes, respectively. Once the participants complete the test session, participants will be crossed over to the alternative treatment. The period between the 2 Phases will not be longer than one week.

Table 1: Study Overview

Procedures	Study Phases	

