*Saline infusions will follow each nicotine infusion to maintain a 10-min total infusion time for each test session. Abbreviations: CO: Alveolar carbon monoxide; HR/BP: Heart rate/Blood pressure; M-NWSC: Minnesota Nicotine Withdrawal Symptom Checklist; BQSU: Brief Questionnaire of Smoking Urges; CPT: Continuous Performance Test; DEQ: Drug Effects Questionnaire; SAFTEE: Systematic Assessment for Treatment Emergent Events. MCP: Money choice procedure.

7) Statistical analysis and sample size estimates

Specific Aim #1: To examine if switching from menthol to non-menthol cigarettes will change the dose-effect curves for positive subjective effects and alleviation of smoking urges as a function of nicotine delivery rate.

Positive subjective effects of nicotine will be assessed with the “Like the Drug Effects” and “Good Drug Effects” items from the DEQ, consistent with the FDA Guidance on abuse potential assessment (10). These items have been shown to correlate with the abuse potential of drugs of abuse. Effects will be tested using linear mixed effects models with peak change on each DEQ item as a response variable, cigarette-assignment (menthol vs. non-menthol), phase (1 vs.2) and nicotine delivery condition as within-subject factors and their interaction. Random effects for subject and condition within subject will be used to account for correlations between

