repeated measures. Because of the potential skewed distributions of the subjective effects data, transformations will be applied as necessary. We will evaluate the main and interactive effects of cigarette assignment and delivery rate. We anticipate statistically significant main effects of cigarette assignment, nicotine delivery rate and a significant interaction between cigarette assignment and nicotine delivery rate. To better understand the dose effects of nicotine delivery rate and whether they are moderated by cigarette assignment, we will construct specific contrasts among the four doses to test whether there is an indication of significant linear, quadratic, linear on log-scale or sigmoidal dose-response relationships across, or within menthol-preference groups. The possible dose-response curves identified by the specific mean contrasts will be compared by fitting linear and non-linear (as necessary) dose-response models with continuous dose and selecting the best-fitting model by the Akaike's Information Criterion (AIC). To test for an effect of delivery rate on smoking urges, assessed by the BQSU (Factor 1 and 2) scores, we will use similar modeling approach described for subjective effects, but we will also include time as a within-subject factor with outcomes for minute 0, 10, 30, 60 and 120. We anticipate a significant main effect of menthol-preference, nicotine delivery rate and potentially a significant interaction between cigarette assignment and nicotine delivery rate.

Exploratory Aim#1: To explore the dose-effect curves of nicotine delivery rate for a) reinforcement (assessed with the Multiple-Choice Questionnaire), b) heart rate and blood pressure, and c) tobacco withdrawal severity, assessed with self-report symptoms and cognitive performance.

The primary outcome for the analysis of reinforcement will be the crossover point determined by the monetary choice procedure for the four infusion conditions. The crossover point is the monetary value at which a subject chooses money over receiving the infusion for that condition. It is a continuous measure (dollar amount) from -20 to +20 with values > \$0 indicating reinforcement. Tobacco withdrawal severity is measured by the MNWS and CPT taken at 0, 30, 60 and 120 min after the beginning of infusion. The models will be similar to the one described for Specific Aim #1 with time as an additional within-subject factor for heart rate, blood pressure and tobacco withdrawal severity.

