Exploratory Aim#2: To examine the impact of plasma nicotine levels and rate of nicotine metabolism (measured by plasma hydroxy cotinine/cotinine ratio) on the dose-effect curves for the main study outcomes.

To address this aim, we will use a similar mixed model approach to the one described for specific aim #1. For plasma nicotine levels, we will include peak plasma and area under the curve (AUC) nicotine plasma concentration as a continuous predictor instead of nicotine delivery condition in separate mixed models. The AUC will be calculated using the nine nicotine concentrations collected across the 120-minute sampling period.

For the rate of nicotine metabolism, the plasma hydroxy cotinine/cotinine ratio will be included as a continuous predictor in the model.

Exploratory Aim#3: To examine sex differences for the main study outcomes.

To evaluate whether sex moderates' menthol and nicotine delivery rate effects we will add sex as an additional factor in all models above.

Rationale for sample size: With 30 individuals, the study will have over 80% power to detect large effect sizes ($f=0.4$) for the comparisons of the menthol and non-menthol conditions ($f=0.6$ or higher) on alleviation of the subjective effects and similarly large effect sizes for the interaction between condition and nicotine delivery rate ($f=0.65$ or higher) at Bonferroni-adjusted level of 0.025. To account for 20% dropout, we will recruit approximately 38 subjects.

11. Risks and benefits:

Potential risks

There are potential risks, discomforts and inconveniences associated with the participation in this study. These may be due to nicotine administration, blood drawing, and other study procedures.

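### The Aim 1 mixed models name one undefined random term besides subject; read as a single intercept, it leaves at least one main-effect test too liberal and distorts the interaction test

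*Combined protocol and SAP*

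**What the plan says.** All references are to the combined protocol and SAP.

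- **Design.** Under *Overview of the study*: "In week 2 of each Phase, participants will have a test session". There is one phase per cigarette type, so session and cigarette assignment coincide within a person. Under *Nicotine administration*: "In each test session, there will be a total of 3 infusions", two at nicotine rates and one saline. That is 2 × 3 = 6 infusions per person.
- **DEQ model** (section 7, *Statistical analysis and sample size estimates*, Specific Aim #1): "linear mixed effects models with peak change on each DEQ item as a response variable", so one value per infusion. The fixed part has cigarette assignment, "phase (1 vs.2) and nicotine delivery condition as within-subject factors and their interaction". The random part is: "Random effects for subject and condition within subject will be used to account for correlations between" repeated measures.
- **Smoking urges (BQSU), same aim:** a similar approach, but "we will also include time as a within-subject factor with outcomes for minute 0, 10, 30, 60 and 120". The random effects are not restated.
- **Exploratory Aim #1**, on withdrawal severity, blood pressure and heart rate: "The models will be similar to the one described for Specific Aim #1 with time as an additional within-subject factor".

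'Condition' is used for different things. Just before the random-effects sentence it is the nicotine delivery condition. In Exploratory Aim #1 it denotes the infusion. In the sample-size rationale it is the cigarette: "for the interaction between condition and nicotine delivery rate".

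**The concern.** Three kinds of variation arise within a person: between sessions, between delivery conditions, and between individual infusions. Cigarette assignment changes only between sessions, so its test needs session-to-session variation in the error. The delivery test needs subject-by-delivery variation. The assignment × delivery test needs infusion-level variation, which is the residual when there is one value per infusion but a separate layer when there are several.

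The plan names one term where the DEQ model needs two and the BQSU model three. An omitted component falls into the residual. The main effect that should have been judged against it then gets too small an error, and the DEQ interaction gets too large a one. The interaction matters because Hypothesis #1 concerns a shift in dose-effect curves. An undefined term also lets the error structure be chosen after the data are seen.

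**Working it through.** **The plan's own figure.** The sample-size rationale claims over 80% power with 30 people at 0.025, for f=0.6 (cigarette) and f=0.65 (interaction). With noncentrality n·f²:

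- Cigarette, f=0.6 as a paired effect: 81.6%.
- Interaction (2 df), 30 × 0.65² = 12.675: 81.5% with F(2,58), 81.4% with F(2,56).
- Dropout: 30/0.8 = 37.5, so 38.

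The figures reproduce if the correct error term is used.

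**Inputs.** n=30 in a balanced two-sequence crossover, 2 sessions × 3 infusions, T readings per infusion (T=1 for peak DEQ; T=5 for the SAP's BQSU times). Assumed, since the documents give none: residual variance 1; session (s), subject-by-delivery (d) and, for T>1, infusion (i) variances all equal, at 0, 0.25, 0.5 or 1.

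**Expected mean squares**

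| Stratum | Expectation | df |
|---|---|---|
| Session | 1 + T·i + 3T·s | 28 |
| Subject × delivery | 1 + T·i + 2T·d | 56 |
| Infusion | 1 + T·i | 56 |
| Within infusion | 1 | 168(T−1) |

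Each reading of 'condition' pools the strata it does not separate. With balanced data this matches REML, away from zero variance estimates. Rejection rates come from simulating these mean squares.

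**DEQ peak, components 0.5.** Session mean square 1 + 3(0.5) = 2.5; delivery 1 + 2(0.5) = 2.0; infusion 1.

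- *Delivery reading:* pooled error (28×2.5 + 56×1)/84 = 1.5. Cigarette ratio 2.5/1.5 = 1.67, interaction 1/1.5 = 0.67.
- *Cigarette reading:* pooled error (56×2 + 56×1)/112 = 1.5. Delivery ratio 2/1.5 = 1.33, interaction 0.67.
- *Six-cell reading* (the term is the residual): (70 + 112 + 56)/140 = 1.7. Ratios 1.47, 1.18 and 0.59.

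Actual type I error at nominal 2.5%, as components go from 0.25 to 1:

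| Reading | Cigarette | Delivery | Interaction |
|---|---|---|---|
| Delivery | 6–11% | 2.5% | 0.1–1.1% |
| Cigarette | 2.5% | 5–8% | 0.1–1.1% |
| Six cells | 5–8% | 4–5% | under 1% |
| All terms named | 2.5% | 2.5% | 2.5% |

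Power of the DEQ interaction test at f=0.65 falls from 81% to about 73%, 62% and 42% at components 0.25, 0.5 and 1 under the delivery or cigarette reading, and to 69%, 55% and 29% under the six-cell reading.

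**BQSU, T=5, components 0.5.** Session 1 + 2.5 + 7.5 = 11; delivery 1 + 2.5 + 5 = 8.5; infusion 3.5; within infusion 1 on 672 df.

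- *Delivery reading:* (308 + 196 + 672)/756 = 1.56. Cigarette ratio 7.1, interaction ratio 2.25.
- *Cigarette reading:* (476 + 196 + 672)/784 = 1.71. Delivery ratio 5.0, interaction ratio 2.04.
- *Six-cell reading:* (308 + 476 + 196)/140 = 7.0. Ratios 1.57, 1.21 and 0.50.

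Over components 0.25 to 1:

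| Reading | Cigarette | Delivery | Interaction |
|---|---|---|---|
| Delivery | 30–48% | 2.5% | 12–27% |
| Cigarette | 2.5% | 35–57% | 11–22% |
| Six cells | 7–8% | 4–5% | under 1% |
| All terms named | 2.5% | 2.5% | 2.5% |

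Table 2 schedules BQSU three times after the start of each infusion (10, 30 and 45 minutes, plus 180 minutes at session end), not at the SAP's five times. With T=3 the affected main effect is 20–36% (cigarette) or 21–40% (delivery), and the interaction about 6–13%.

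With all components at zero, every reading gives 2.5%.

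**The case against.** - **Is this only missing detail?** The documents call both factors conditions, and the plural 'random effects' could mean one effect per factor, or an unstructured covariance over the six cells. Nothing excludes these, so a reader who infers that the plan can never cover both layers goes too far. But neither is stated. One effect per factor would still lack an infusion term in the time models (interaction error about 16–42% at T=5). An unstructured six-cell covariance has 6×7/2 = 21 parameters for 30 people.
- **Is every Aim 1 test wrong?** No, tempting as that inference is. The delivery test is correct under the delivery reading and the cigarette test under the cigarette reading.
- **Is infusion always omitted once time is added?** No. Under the six-cell reading the term is the infusion. What remains missing is session and delivery, with the much milder main-effect errors shown above.
- **Is the DEQ interaction prone to false positives?** No, it is conservative. That is a loss of power rather than a defence.
- **Reach.** Heart rate, withdrawal and cognitive performance are exploratory, and blood pressure has about one reading per infusion in Table 2, so the infusion term hardly matters there.
- **Size.** All magnitudes rest on assumed variances. The interaction inflation in time models needs appreciable infusion variance: with four readings and the other components at 0.5, an infusion variance of 0.1 leaves it near 2%.

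**Conclusion.** The point holds as a defect in the stated random-effects structure and should be settled before analysis. Under any single-intercept reading, at least one Aim 1 main-effect test is anti-conservative whenever the omitted variance exceeds zero, and the DEQ interaction test then loses power. In the BQSU model, the delivery and cigarette readings also leave out infusion, which makes the interaction test anti-conservative when infusion variance is material. The direction follows from the design; the percentages are illustrations for balanced data with n=30. Zero omitted variance would remove the problem, but the two sessions fall in different two-week phases on different cigarettes, and the *Significance* section itself stresses individual differences in response to delivery rate, so the plan should not rely on zero. A reader might infer that the sample size must change. This point alone does not require it: with the right error terms the 30 and 38 stand on the plan's own f=0.6 and f=0.65.

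**What to change.** Replace the random-effects sentence in Specific Aim #1 with: random intercepts for subject, for session (phase) within subject, and for delivery condition within subject; in every model with repeated times, also for infusion within session; Kenward-Roger degrees of freedom. An equivalent covariance is acceptable if it is written out. State that the same structure carries over to BQSU and to the Exploratory Aim #1 models with time.

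The cost is one sentence and a few lines of code. The downside is fewer denominator degrees of freedom (for DEQ, 28 rather than 84 for cigarette under the delivery reading, and 56 rather than 112 for delivery under the cigarette reading) and wider intervals for the main effects. A parallel analysis on each person's own contrast, adjusted for phase, is a useful check but optional.

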ClinicalTrials.gov ID: NCT04535362
Brief Title: Nicotine's Potential Abuse With Menthol
Date: 6.16.2023
Document: Protocol w SAP

1. Principal Investigator: [name]., Ph.D.

2. Co-Investigators While all research staff are trained to provide informed consent, those identified with an asterisk (*) will provide informed consent for this study. All the research staff will have access to the PHI

Co- Investigator: [name].

Nursing Staff: *[name], [name], R.N.,

Research Staff: *[name], BS, and *[name]

3. Title of Project: Impact of Menthol on the Abuse Potential of Nicotine

4. Purpose, hypothesis and key questions:

Specific Aim: To examine if switching from menthol to non-menthol cigarettes will change the dose-effect curves for positive subjective effects and alleviation of smoking urges as a function of nicotine delivery rate in smokers.

Hypothesis #1: Switching to non-menthol cigarettes, compared to smoking menthol cigarettes, will enhance responses to nicotine for both positive subjective effects and alleviation of smoking urges as reflected by a leftward shift in dose-effect curves.

Exploratory Aims:

Exploratory Aim#1: To examine if switching from menthol to non-menthol cigarettes will change the dose-effect curves of nicotine delivery rate for a) reinforcement (assessed with the monetary value of the dose from the Multiple-Choice Procedure, b) heart rate and blood pressure, and c) tobacco withdrawal severity (assessed with self-report symptoms and cognitive performance).

Exploratory Aim#2: To examine the impact of plasma nicotine levels and rate of nicotine metabolism (measured by plasma hydroxy cotinine/cotinine ratio) on the dose-effect curves for the main study outcomes.

Exploratory Aim#3: To examine sex differences for the main study outcomes.

5. Background:

Nicotine control policies to reduce the addictive potential of tobacco products:

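### Specific Aim #1 does not say whether the open-label assignment main effect or the assignment-by-delivery interaction decides Hypothesis #1, and a uniform shift in self-ratings could produce the main effect alone

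*Combined protocol and SAP*

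**What the plan says.** Section 4, Hypothesis #1, predicts that switching to non-menthol cigarettes "will enhance responses to nicotine for both positive subjective effects and alleviation of smoking urges as reflected by a leftward shift in dose-effect curves". The claim concerns the response to nicotine, not the general level of ratings.

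On blinding, the Overview of the study states: "The smoking condition will be open label". Menthol is the participant's usual brand, and non-menthol is a matched-brand product. Only the infusions are masked: "Participants will be blind to the order of nicotine infusions" (Nicotine administration). Each session gives nicotine, saline, then nicotine, with saline always second (Overview; Table 2).

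For the DEQ Like and Good Effects items, section 7, Specific Aim #1, plans "linear mixed effects models with peak change on each DEQ item as a response variable", with "cigarette-assignment (menthol vs. non-menthol), phase (1 vs.2) and nicotine delivery condition as within-subject factors and their interaction". It will evaluate both main and interactive effects. The expectation "We anticipate statistically significant main effects of cigarette assignment, nicotine delivery rate" is followed in the same sentence by an expected significant interaction of assignment with delivery rate.

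For BQSU the approach is similar, with time added at minutes 0, 10, 30, 60 and 120. Here a main effect is expected and an interaction is only a possibility. The text calls that main effect one of menthol preference; since only menthol smokers are recruited, I read it as assignment.

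The Rationale for sample size claims over 80% power with 30 individuals at 0.025, both for "comparisons of the menthol and non-menthol conditions" (f=0.6) and for the interaction (f=0.65).

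**The concern.** Participants know which cigarettes they are smoking, and the outcomes are their own ratings. Expectancy, feelings about giving up the preferred brand, or a changed rating habit could move ratings after every infusion, saline included. Such a shift enters the assignment main effect in full, whereas a true change confined to nicotine enters at two thirds. The shift could point either way: it could imitate enhancement, or hide or reverse a real one.

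The interaction would not react to a uniform shift. But the plan lists both terms as expected findings under one hypothesis and gives no rule for the case where only the main effect is significant.

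For BQSU, a main effect without an interaction would match the stated expectation. A smoker whose urge is higher at every reading, including before any infusion, has a level shift, not a change in alleviation. The study is presented as a short-term model of a menthol ban (section 6), so the distinction affects its policy reading.

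**Working it through.** **1. The plan's power figures.** Inputs are N=30, alpha 0.025, f=0.6 and f=0.65 (Rationale for sample size). I used a noncentral F with λ = N·f².

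- Main effect: λ = 30 × 0.36 = 10.8; with 1 and 28 or 29 df, power is about 81.5%.
- Interaction: λ = 30 × 0.4225 = 12.675; with 2 and 58 df, power is 81.5%. With 3 numerator df (3 and 87) it is 76.4%.
- Dropout: 30/(1 − 0.20) = 37.5, so 38.

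Both power claims reproduce, so the two terms are powered alike. The interaction figure fits 2 df, that is, three delivery conditions including saline. On that reading the main effect averages over saline. (The f=0.4 in the same sentence gives only 44% for the main effect on this convention.)

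**2. What each test measures.** Let s be the residual SD and t the subject-by-phase SD. For the difference between phases within a participant:

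- Main effect: variance 2(s²/3 + t²). A uniform shift enters in full; a nicotine-only effect enters at 2/3.
- Nicotine-minus-saline contrast: variance 2(1.5s²) = 3s². A uniform shift contributes 0; a nicotine-only effect enters in full.

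**3. Assumptions.** The documents give no SDs. I take the 100 mm scale, s = 15 to 20 mm, t = 10 mm, 30 completers and a two-sided paired t test at 0.025.

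| | s=15 | s=20 |
|---|---|---|
| SD of main effect | √350 = 18.7 | √466.7 = 21.6 |
| SD of contrast | √675 = 26.0 | √1200 = 34.6 |
| Uniform 5 mm shift, no nicotine change: main effect significant | 20% | 15% |
| Uniform 10 mm shift, no nicotine change: main effect significant | 71% | 57% |
| Uniform shift, any size: contrast significant | 2.5% | 2.5% |
| True 15 mm nicotine-only effect: main effect (signal 10 mm) | 71% | 57% |
| Same: contrast (signal 15 mm) | 78% | 51% |
| Same: planned 2-df interaction | 70% | 42% |

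For the last row the effects are (0, 15, 15), the squared deviations from their mean sum to 150, and λ = 30 × 150/(2s²) = 10 or 5.625.

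A simulation in residual-SD units (N=30, session SD 0.5) agrees: a uniform shift of 0.4 SD makes the main effect significant in 38% of trials and the interaction in 2.6%. With session SD from 0 to 1.0, the 38% ranges from 63% to 17%.

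**4. When the contrast costs power.** It is weaker than the main effect when (2/3)²/[2(s²/3 + t²)] > 1/(3s²), that is, when t < s/√3. The threshold is 8.7 mm at s=15 and 11.5 mm at s=20. At s=20 the comparison is 51% against 57% for t=10, and 51% against 83% for t=0.

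**5. What the contrast does not remove.** If expectancy adds 10 mm after nicotine and 2 mm after saline, the contrast carries 10 − 2 = 8 mm of false signal and is significant 27% (s=15) or 15% (s=20) of the time.

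**6. BQSU timing.** Table 2 has BQSU at baseline, minute 45 and minute 105, so each infusion has an earlier reading to use as reference. The model instead keeps minute 0 among the outcomes, and nothing states that the assignment effect is to be judged on change from it.

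**The case against.** A reader might infer that the plan rests Hypothesis #1 on the main effect alone, or has no control for expectancy. The documents do not support that. For DEQ the interaction is equally anticipated and equally powered, and with saline as a level of delivery condition it already removes a uniform shift. The hypothesis is framed as a shift in dose-effect curves, and Specific Aim #1 plans contrasts and curve fits to see whether assignment moderates them. Nowhere is the main effect said to suffice. What is missing is a decision rule, not a test.

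The DEQ response is peak change, which would cancel a shift already present before infusion. This helps only partly: Table 2 lists no baseline DEQ (the Test Session text mentions only self-report assessments), and a baseline cannot cancel expectancy about how the infusion will feel. Likewise, time in the BQSU model makes level and change separable, but the plan does not say that the inference rests on the separation.

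Annoyance at losing the preferred brand might well lower liking under non-menthol, against the hypothesis. That is fair. The documents fix no direction, so the figures above are rates of a significant result in either direction, not rates of false support.

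Saline is an imperfect reference. It always follows nicotine by an hour, and the plan itself acknowledges carry-over. For BQSU the minute-45 reading comes after Infusion 1, so a rebound from stronger relief would enter the saline change. This stands and calls for a sensitivity analysis.

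Finally, the plan speaks of four doses where the design has three infusion conditions. The two-thirds weight assumes three.

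**Conclusion.** The concern holds as an unspecified decision rule. Two terms are evaluated, anticipated and powered for one hypothesis, and one of them can be produced by a uniform shift in open-label self-ratings. Under the assumed SDs, that happens 15% to 20% of the time for a 5 mm shift and 57% to 71% for 10 mm. The sizes are illustrative; the direction of the argument does not depend on them. It does depend on saline being a level of delivery condition, which the design and the 2-df power match support.

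The gap is moderate for DEQ, where the interaction is an explicit expectation, and sharper for BQSU. It would also be too strong to read the saline-referenced contrast as immune to expectancy: it removes the additive part only. The change should be made before the data are analysed, but the design itself is not undermined.

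**What to change.** State in Specific Aim #1 that:

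- **DEQ Like and Good Effects:** Hypothesis #1 is judged by one contrast in the planned model, (mean of the two nicotine infusions minus saline) under non-menthol minus the same under menthol.
- **BQSU:** the same contrast is applied to post-infusion scores adjusted for, or expressed as change from, the last reading before each infusion (baseline, minute 45, minute 105). Because saline always follows nicotine, add a sensitivity analysis of Infusion 1 change from session baseline.
- **Main effect of assignment:** descriptive only.
- **Expectancy check:** report saline and pre-infusion ratings by assignment.

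Reconcile the four doses in the text with the three infusion conditions, so that the contrast weights are unambiguous.

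The cost is SAP wording; model and data are unchanged. The downside is lower power than the main effect whenever the subject-by-phase SD is below the residual SD/√3, as quantified above. Under the same assumptions the single contrast has more power than the planned 2-df interaction when the effect is equal at both nicotine rates. Expectancy that scales with felt drug effect remains a limitation to state in the report.
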